## 9.2. Study Drug Dose Levels

The dose levels are outlined in Table 2. The dose escalation at Study Day 15 (start of Week 3) will occur at the patient's home. The site will call the patient to confirm that the escalation has occurred and to record any AEs.

Table 2: Study Drug Dose Levels by Study Week and Patient Age

Study Week	For Patients 6 up to 16 Years Old (mg/day)	For Patients ≥ 16 Years Old (mg/day)
1 and 2	1.0	2.0
3 and 4	2.0	3.0
5 to 16	3.0	

Dose levels may deviate from this plan after consultation with the Sponsor, if necessary due to an AE, or other safety or tolerability concern. No dose greater than 3.0 mg per day will be administered during this study. Additionally, patients who are currently enrolled in this study at the time of this protocol amendment, and who are not currently at a dose of 3.0 mg per day, will be assessed by the Primary Investigator and the Sponsor to determine if an increase in the dose to 3.0 mg per day is appropriate.

## 9.3. Blinding

This study will be open-label, so there is no blinding.

## 9.4. Packaging and Labeling of Study Drug

All study drug will be labelled as per the local regulations and provided in a cardboard box that contains a single vial.

## 9.5. Handling and Storage of Study Drug

All study drug must be kept in a secure, limited-access storage area at a temperature between 2°C and 8°C. Setmelanotide is stable at room temperature for a short period that will allow patients to transport study drug home; ice packs and cooler bags will be provided to patients to transport the

drug to their home. Once home, the un-opened study drug must be stored in the patient's refrigerator. Opened study drug may be stored at room temperature for up to 30 days.

## 9.6. Assessment of Treatment Compliance and Study Drug Accountability

Accountability for the study drug at the study site is the responsibility of the Investigator. The Investigator will ensure that the study drug is used only in accordance with this protocol. Where allowed, the Investigator may choose to assign drug accountability responsibilities to a pharmacist or other appropriate individual. Drug accountability records indicating the delivery date to the site, inventory at the site, use by each patient, return of all used study drug to the study center, and return to Rhythm (or disposal of the drug, if approved by Rhythm) will be maintained by the clinical site. Reasons for departure from the expected dispensing regimen must also be recorded. The Sponsor or its designee will review drug accountability at the site during monitoring visits.

Compliance to dosing will be monitored throughout the study by having the patient complete a daily dosing log that records daily dosing information, including the time of dosing, location of the injection, and the amount of drug dosed. If a patient is non-compliant with the dosing schedule, the Sponsor may implement steps to ensure compliance, e.g., sending a nurse to the patient's home for retraining or having a nurse administer the study drug.

## 9.7. Prior and Concomitant Treatment

#### Prohibited Medication and Substances

Unless concomitant medications are likely to present a strong potential safety concern, the general goal of this protocol is to allow as many patients with these ultra-rare conditions to participate in the study as possible.

Medications that are approved to treat obesity (e.g., orlistat, lorcaserin, phentermine-topiramate, naltrexone-bupropion) are not allowed within three months of first dose of study drug (e.g., enrollment) and are prohibited during the course of the study.

GLP-1 receptor agonists may be used up to the dose approved for the treatment of diabetes mellitus (e.g., liraglutide up to a daily dose of 1.8 mg) as long as (1) it is not being prescribed for the treatment of obesity, (2) the dose has been stable for at least three months prior to enrollment, (3) the patient has not experienced weight loss during the previous three months, AND (4) the patient intends to keep the dose stable throughout the course of the study.

Other medications that may cause weight loss (e.g., stimulants) are allowed as long as the patient (1) has used a stable dose for at least three months prior to enrollment, (2) has not lost weight during the previous three months, and (3) intends to keep the dose of the medication stable through the course of the study.

All concomitant medications should be kept at a stable dose throughout the course of the study, unless a dose change is necessary to treat an AE.

Protocol Amendment 10 RM-493-014

## 10. SCHEDULE OF ASSESSMENTS

The Schedule of Assessments (SOA) is presented in Table 3.

**Table 3:** Schedule of Assessments

Study Period/Procedure	Screening	Study Treatment			EOS Visit	Bridging Visit(s) 31				
Clinic Visit Number	V1	V2	-	V3 	V4	V5	V6 30	V7	+ up to 12 weeks from V6	Treatment Discontinuation
Start of Week X	-8 to -2	0	2	4	8	12	16	20	(up to one year	Visit
Study Day (± 3 days)	-56 to -14	1	15	29	57	85	113	141	from V6)	
Sponsor review of patient genetics/Genetic Testing 	X									
Informed consent/Assent 33	X									
Inclusion/Exclusion review	X	X								
Medical history review	X									
Physical examination 	X	X		X	X	X	X	X	X	X
Comprehensive skin exam 	X						X			X
Fitzpatrick classification scale	X						X	X		X
Hepatic imaging 	X									
Weight 	X	X		X	X	X	X	X	X	X
Waist circumference 	X	X		X	X	X	X	X	X	X
Height 	X			X	X	X	X	X	X	X
Vitals 	X	X		X	X	X	X	X	X	X
ECG (12-lead) 9	X	X 		X			X		X	X
Pregnancy test 	X	X 32		X	$X^{32}$	$X^{32}$	$X^{32}$		$X^{32}$	$X^{32}$
Daily hunger questionnaires 11	X			•	Daily	32	•			$X^{32}$
Global hunger assessment 12		$X^{32}$		X 	$X^{32}$	$X^{32}$	X 	X	$X^{32}$	$X^{32}$

Table 3: Schedule of Assessments (Continued)

Study Period/Procedure	Screening			Study T	reatme	nt		EOS Visit	Bridging Visit(s) 31		
Clinic Visit Number	V1	V2	-	V3 	V4	V5	V6 30	V 7	+ up to 12 weeks from V6	Treatment Discontinuation	
Start of Week X	-8 to -2	0	2	4	8	12	16	20	(up to one year from V6)	Visit	
Study Day (± 3 days)	56 to 14	1	15	29	57	85	113	141	from vo)		
Safety laboratory tests 19	X	X		X 	X 	X 	X 	X	$X^{32}$	$X^{32}$	
Anti-drug antibody samples	X	X		X			X	X	X	X	
Injection site inspection 		X		X	X	X	X		X	X	
Telephone call 			X								
Study drug administration 				Daily	dosing		-		X		
Dispense/Return study drug 		X		X	X	X	X		X		
Adverse event assessment 	X	X	X	X	X	X	X	X	X	X	

**Table 3:** Schedule of Assessments (Continued)

Study Period/Procedure	Screening	Study Treatment					EOS Visit	Bridging Visit(s) 31		
Clinic Visit Number	V1	V2	-	V3 	V4	V5	V6 30	V7	+ up to 12 weeks from V6	Treatment Discontinuation Visit
Start of Week X	-8 to -2	0	2	4	8	12	16	20	(up to one year from V6)	
Study Day (± 3 days)	56 to 14	1	15	29	57	85	113	141	nom voj	
Concomitant medications review	X	X	X	X	X	X	X	X	X	X

V, Study Visit Number; EOS, End of Study;

- 1. Prior to conducting any screening assessments, Sponsor will review and approve the specific genotype to ensure it meets the criteria for the patient populations included in the study (Section 11.1).
- 2. A complete physical examination will be conducted at Screening and at the EOS V7. At other timepoints, an abbreviated examination will be performed. The abbreviated examination should focus on heart, lungs, skin, neurologic exam, and any areas of previous abnormal findings, noting any changes from baseline. In addition, for assessment of pubertal development will be conducted for those patients who have yet to reach whenever possible, the same trained health care professional will conduct the exam and (Section 11.5).
- 3. A comprehensive skin evaluation will be performed by a dermatologist. The skin exam should include a full body skin exam (head-to-toe skin examination) from a trained and licensed dermatologist. Any concerning lesions identified during the Screening Period will be biopsied and results known to be benign prior to first dose of setmelanotide. If the pre-treatment biopsy results are of concern, the patient will be excluded from the study. Additionally, any lesion or change in an existing lesion during the course of the study must be evaluated by the dermatologist and biopsied, if clinically indicated in the opinion of the dermatologist. Any biopsies must be evaluated by a trained dermatopathologist, and biopsy reports must be part of the study information for each patient (Section 11.6).
- 4. Weight (kg) is to be measured at the clinic using the same scale throughout the study, after patients have emptied their bladders and bowels and after fasting for at least 8 hours. Patients are to wear light clothing or underwear and no shoes, and will be weighed at approximately the same time of day. Weight measurements are to be done in triplicate (Section 11.8).
- 5. Waist circumference (cm) will be single measures (Section 11.9).
- 6. For patients ≥18 years of age, height needs to be measured at the screening visit only. Height (cm) will be measured, without shoes, socks, or hats, using a wall-mounted stadiometer. All measurements will be done in triplicate at each timepoint and recorded to the nearest 10th of a decimal place (Section 11.10).
- 8. All BP and HR measurements are to be obtained in the sitting position following at least 5 minutes of rest. All measurements will be taken in triplicate, approximately 2 minutes apart. When possible, BP should be taken in the non-dominant arm throughout the study, using the same

methodology (automated or manual). Body temperature (°C) and respiration rate (breaths/minute) will be obtained in the sitting position following at least 5 minutes of rest (Section 11.13).

9. A single 12-lead ECG will be performed in the supine position following a period of at least 10 minutes of rest (Section 11.14). At visit 2 the ECG will be performed before and 8 hours after dosing.

10.	A urine pregnancy test may be performed to expedite availability of results prior to dosing on Day 1. All other pregnancy tests will be serum tests (Section 11.15); dosing may continue with results pending.
19.	Safety laboratory tests will include: CBC with platelet count and standard indices, chemistry panel (includes sodium, potassium, chloride, CO 2 , albumin, total protein, glucose, BUN, creatinine, uric acid, AST, ALT, GGT, CPK, alkaline phosphatase, total bilirubin, direct bilirubin, LDH,
	calcium, phosphorus), and urinalysis with microscopic analysis if positive findings on dipsticks warrant further examination. Safety laboratories will also include a coagulation profile (PT or INR, and PTT also referred to as aPTT).

- 23. Blood samples will be collected prior to dose administration in the
- 24. Injection site evaluations and scoring (by the clinical staff) will include identification and measurement of areas of erythema, edema, and induration, as well as the presence of localized pain, tenderness, and itching. Additional evaluation data can be collected at any visit in which there are injection site reactions, even if not a timepoint for formal assessment (Appendix A).
- 25. Site should call the patient to confirm the proper dose escalation has occurred, and to collect AEs.
- 26. Patients/caretakers will draw up and self-administer/administer the drug once daily in the morning beginning the morning of Day 1 and for the duration of dosing. On days with clinic visits, the patients/caretakers will administer the drug in the clinic in the presence of the clinical staff to assure proper technique.
- 27. Patients/caretakers will return all (the number recorded) used vials to the clinic when they visit, and both clinic-administered study drug as well as outpatient study drug administration will be recorded in a study diary.
- 28. Adverse events will be recorded from the time a patient provides informed consent. AEs reported after dosing on Day 1 will be considered treatment-emergent AEs.
- 29. Patients who are <16 years of age will receive first daily dose of 3.0 mg at V3, at clinic site.
- 30. Study endpoints are analyzed at V6. After completing V6, patient enters a separate extension study (Protocol RM-493-022), does not enter the extension study and returns for the final study Visit 7 in 4 weeks, or completes Bridging Visits for up to one year or until the extension study is initiated.
- 31. Bridging Visits only needed if separate extension study RM-493-022 is not initiated at site at the time of V6.
- 32. Collected prior to study drug administration.
- 33. Although the study procedures and assessments required per protocol are classified as "No or Minimal Risk" (with the exception of may be classified as "Minor Increase over Minimal Risk") according to the 2008 Guidance Document "Ethical Considerations for Clinical Trials on Medicinal Products Conducted with the Pediatric Population," considerations for reducing pain in distress in participants younger than 18 years of age are included in Appendix J.
- 35. Only applicable to SCR1 patients.
- 36. During visit 2 ECG will be collected prior to dosing and ~8 hours post-dose.

### 11. PATIENT ASSESSMENTS AND REQUIREMENTS

#### Order of Assessments

When scheduled at the same time point, the order of procedures should be as follows: obtain vital signs, perform 12-lead ECG, and perform blood draws (at the specified time point, if applicable). Adjustments may be made depending upon specific circumstances and in consultation with the Sponsor.

### 11.1. Sponsor Review of Patient Genetics and/or Genetic Testing

The genetic background of each patient must be reviewed by the Sponsor prior to study enrollment to confirm that the patient meets inclusion criteria. For patients that have not had a previous genetic sample taken, a blood sample will be obtained at Screening for genetic confirmation of a genetic disorder of obesity.

In addition, enrollment of patients in some subgroups may be prioritized by the Sponsor in order to ensure enrollment of patients with (1) well described, high-impact genetic mutations, (2) a variety of genetic variants, or (3) genetic variants likely to respond to setmelanotide.

### 11.2. Informed Consent/Assent

A complete description of the study is to be presented to each potential patient, and signed and dated informed consent and/or assent is to be obtained before any study-specific procedures are performed.

### 11.3. Inclusion/Exclusion Review

Inclusion and exclusion criteria are to be reviewed per the SOA (Table 3) to ensure the patient is eligible for the study.

For Exclusion Criterion 9, GFR at Screening will be determined using the Modification of Diet in Renal Disease (MDRD) Equation in patients ≥18 years of age (Appendix H), and the Bedside Schwartz Equation in patients <18 years of age (Appendix I).

# 11.4. Demographics, Concomitant Medications and Medical History Review

Medical history and demographic data including the patient's gender, race, date of birth, and concomitant medication use will be obtained for all patients during the Screening Period (Appendix C).

The medical history should be updated on Day 1 prior to first dose of study drug, to assess continued study eligibility and adherence to final inclusion/exclusion criteria. This medical history update includes a review for changes from Screening as well as a review of the patient's recent medication use to assess whether any changes have occurred since the previous visit.

### 11.5. Physical Examination

A complete physical examination will include review of peripheral lymph nodes, head, eyes (including conjunctiva), ears, nose, mouth and oropharynx, neck, heart, lungs, abdomen, musculoskeletal including back, extremities, and neurologic assessments.

Changes from baseline in any physical examination findings identified by the Investigator as clinically significant must be recorded as an AE on the appropriate electronic Case Report Form (eCRF).

Patients will also be assessed at baseline according to reached will be assessed according to the SOA (Table 3).

## 11.6. Comprehensive Skin Exam

The Investigator will identify a trained and licensed dermatologist to serve as a consultant for the Investigative Site.

The dermatologist will perform comprehensive skin examinations, which should include a full body skin exam (head-to-toe skin examination). Each patient will receive this comprehensive, head-to-toe dermatology examination as part of Screening and prior to the end of the study. Any worrisome lesion should be biopsied prior to study start, and all biopsies must be evaluated by a trained dermatopathologist.

Additionally, any lesion or change in an existing lesion during the course of the study must be evaluated by the dermatologist and biopsied, if clinically indicated in the opinion of the dermatologist. All biopsies must be evaluated by a trained dermatopathologist.

In the event a patient experiences changes to skin or skin lesions that are unresolved (or have not significantly improved or are close to resolution) at the end of study, the patient may be asked to return for additional follow up assessments to document progress towards resolution.

Biopsy reports must be part of the study information for each patient.

#### Protection from Sun

It is also important that patients do not participate in any activities that will intentionally cause their skin to tan (e.g., visit ultraviolet [UV] tanning salons, use spray tanners or self-tanning lotions, etc.).

### 11.7. Fitzpatrick Scale

Each patient is to be categorized for skin type according to the Fitzpatrick scale (Fitzpatrick 1975), depicted in Appendix B.

## 11.8. Weight

Weight (kg) will be recorded as shown in the SOA (Table 3). All measurements will be done in triplicate at each timepoint. Whenever possible, the same scale should be used throughout the study, including the Screening Visit, and should be calibrated on a regular basis. Weight should be

measured at approximately the same time at each visit and after fasting for at least 8 hours. Patients should be in light clothing or underwear, with no shoes, and should have emptied their bladders and bowels.

### 11.9. Waist Circumference

Waist circumference (cm) will be measured according to the National Heart, Lung, and Blood Institute (NHLBI) criteria (NHLBI, 2000) during the study as shown in the SOA (Table 3). All measurements will be single measures. Whenever possible, the same study staff member should perform the measurement for a given patient to minimize variability. Waist circumference should be measured when patients are fasting and at approximately the same time at each visit. Patients should be in light clothing and have emptied their bladders.

### 11.10. Height

Height (cm) will be measured, without shoes, using a wall-mounted stadiometer according to the SOA (Table 3). All measurements will be done in triplicate at each timepoint. Height will be used along with body weight to determine BMI.

# 11.12. Hepatic Fibrosis

Patients entering the study with SRC1 haploinsufficiency obesity must be evaluated during screening with an appropriate imaging test for hepatic fibrosis. Transient elastography and magnetic resonance elastography are both acceptable options for imaging. Other imaging modalities may be acceptable, with approval by the Sponsor. Patients will be excluded from the study if they are

determined by the Primary Investigator to have moderate or greater liver fibrosis (e.g., the equivalent of a METAVIR score  $\geq 2$ ).

### 11.13. Vital Signs

Vital signs will be obtained in the sitting position following at least 5 minutes of rest at the time points indicated in the SOA (Table 3).

### Blood Pressure and Heart Rate

Blood pressure (BP; mmHg) and heart rate (HR; beats per minute [bpm]) evaluations will be performed using the same methodology throughout the study (manual or automated). For a detailed description of the standardized BP measurement to be utilized in this study, see Appendix F.

Special attention should be paid to ensure the appropriate cuff size in this patient population.

Repeat measures and more frequent monitoring can be implemented for significant increases in BP or HR.

To allow for a trough blood pressure reading, the patient should be instructed not to take the study medication on study days when vital signs are to be measured in the clinic.

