#### **Treatment Period**

Eligible patients will return to the clinic within 8-2 weeks of completing the Screening Visit for the Baseline Visit (Visit 2) and first dose of setmelanotide.

Dose levels for all patients will escalate to a final dose of 3.0 mg/day during an initial dose-titration phase, but the starting dose will depend on patient age. Patients 6 up to 16 years old will initially be dosed at 1.0 mg/day for 2 weeks, beginning at the Baseline Visit on Study Day 1. Starting on Day 15, the dose will escalate to 2.0 mg/day and remain at that level for 2 weeks, until the patient returns to clinic for Visit 3 on Day 29. At Visit 3, the dose will be escalated to 3.0 mg/day; the patient will continue dosing at 3.0 mg/day for 12 weeks.

Patients ≥16 years old will initiate dosing at 2.0 mg/day at the Baseline Visit, and continue dosing at that level for 2 weeks. The dose will be escalated to 3.0 mg/day beginning on Study Day 15, and the patient will continue that dose for 14 weeks.

Study site staff will call all patients at their homes after the first 2 weeks of treatment to ensure the escalation occurred as planned and collect any AEs.

Patients will continue dosing at 3.0 mg/day, and return to the clinic every four weeks (Visits 3-5) to complete the assessments in Table 3. After 16 weeks in the study, patients will return to the clinic for Visit 6. At Visit 6, the patient will receive the last setmelanotide injection. Participation in the study will then conclude in one of the following two ways:

• Complete Visit 6 and enroll in a separate extension study, Rhythm Study RM-493-022. If RM-493-022 is not yet open at the clinic site, the patient will continue daily setmelanotide injections and other activities per the current study, as presented in the SOA (Table 3). The patient will return to the clinic for Bridging Visits every 12 weeks for up to one year, until the extension study opens at the site. Additional clinic visits may be scheduled at the discretion of the PI.

[figure not shown]
• Decide not to participate in the extension study and proceed to the final study visit (Visit 7) in 4 weeks.

Patients on study per a previous amendment should transition to dose escalation as outlined in this protocol:

- Patients who are in the dose titration phase and are not currently at a dose of 3.0 mg/day will be assessed by the Primary Investigator and the Sponsor, to determine if an increase in the dose to 3.0 mg/day is appropriate.

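### As worded, Section 11.13 bars study drug on days when vital signs are taken in the clinic, yet the protocol requires a dose on those same visit days

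*Protocol*

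**What the plan says.** The Blood Pressure and Heart Rate part of Protocol Section 11.13 opens with a purpose, "To allow for a trough blood pressure reading", and then states that "the patient should be instructed not to take the study medication on study days when vital signs are to be measured in the clinic". The restriction is framed by study day. It has no qualifier such as before the visit, at home, or until the measurement has been made.

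Table 3 marks vital signs at V1 to V7, at Bridging Visits and at the Treatment Discontinuation Visit. Four statements require a dose on some or all of the on-treatment visits in that list:

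- Table 3 footnote 26: "On days with clinic visits, the patients/caretakers will administer the drug in the clinic in the presence of the clinical staff". SAP Table 2 repeats it.
- Section 7.1, Treatment Period: patients return "for the Baseline Visit (Visit 2) and first dose of setmelanotide".
- Table 3 footnote 29: patients under 16 "will receive first daily dose of 3.0 mg at V3, at clinic site".
- Section 7.1, Treatment Period: "At Visit 6, the patient will receive the last setmelanotide injection".

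Footnote 32, "Collected prior to study drug administration", is attached to entries for pregnancy tests, hunger measures and safety laboratory tests. It is not attached to the Vitals row in Protocol Table 3 or in SAP Table 2.

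**The concern.** Section 11.13 governs what patients are told, and patients or their caretakers normally inject at home each morning. A site that passes on the sentence as written tells the patient not to dose that day. A site that follows footnote 26 doses the patient in the clinic. Each site departs from a written instruction, and about 50 to 75 sites are expected. Non-adherence to the drug regimen is also a listed reason for withdrawal in Section 8.5.

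The second stake is interpretation. Vital signs form part of the safety and tolerability secondary endpoint. SAP Section 4.6.4 summarises actual values and change from baseline by visit, without saying where in the dosing interval the reading falls. The protocol evidently cares about this, since it asks for a trough reading, and its Section 5.3 associates MC4R activation with increases in blood pressure and heart rate.

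**Working it through.** There is no planned figure to reproduce. The check sets the texts side by side, followed by two short counts.

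**Where the instructions meet (Protocol Table 3, footnotes 26 and 29, Section 7.1)**

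| Visit | Study day | Vitals marked | Dose required by footnote 26 | Further text requiring a dose |
|---|---|---|---|---|
| V2 | 1 | Yes | Yes | Section 7.1, first dose |
| V3 | 29 | Yes | Yes | Footnote 29, patients under 16 |
| V4 | 57 | Yes | Yes | None |
| V5 | 85 | Yes | Yes | None |
| V6 | 113 | Yes | Yes | Section 7.1, last injection |
| Bridging | Variable | Yes | Yes | Table 3 study drug row |

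V1, V7 and the Treatment Discontinuation Visit carry vital signs but no scheduled dosing, so they do not conflict. The overlap is 5 of 5 scheduled on-treatment visits, plus every Bridging Visit.

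**Size under the literal reading.** Day 1 to Day 113 is 113 dosing days, and 5 / 113 = 4.4%. If the visits with their own specific dosing text are set aside (V2 and V6 for everyone, V3 for patients under 16), what remains is:

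- patients under 16: V4 and V5, 2 / 113 = 1.8%
- patients 16 and over: V3, V4 and V5, 3 / 113 = 2.7%

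**Does other text settle the order?** Section 11 (Order of Assessments) puts vital signs first, the ECG second and blood sampling third when they share a time point. Section 11.18 has safety blood and urine samples taken before dosing. Table 3 schedules safety laboratory tests at V2 to V6 and at Bridging Visits. Vital signs precede blood draws and blood draws precede dosing, so the default is a pre-dose reading. Two gaps remain. Section 11 does not mention dosing and allows the order to be adjusted in consultation with the sponsor. And an order of events within a visit does not remove a prohibition that covers the whole day.

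**Comparison with the earlier schedule.** The SAP's pre-amendment 9 tables do tie vital signs to dosing: entries in the active-treatment and extension tables carry a pre-dose footnote, and footnote 16 specifies pre-dose and then roughly hourly readings on Day 1 and on titration days. The current schedule has no equivalent for vital signs, although it does state pre-dose and about 8-hour timing for the V2 ECG.

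**Effect on the primary analysis window.** SAP Section 4.3.1 dates the first therapeutic dose to Visit 3 for post-amendment 9 patients and accepts visits 60 to 120 days later. V6 falls 113 − 29 = 84 days after V3. If the V3 dose were omitted and dosing at that level began the next day, the interval would be 113 − 30 = 83 days, still inside the window.

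**The case against.** The strongest reply is that the purpose clause resolves the matter. A trough reading is one taken before the next dose. The instruction is addressed to patients who usually inject at home in the morning, and footnote 26 moves visit-day dosing into the clinic under observation. Taken together, the texts can be read as telling the patient not to inject before coming in. The sequence in Sections 11 and 11.18 points the same way.

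Most of this stands. It makes a wording fault more likely than a conflict of design, and it counts against two stronger readings that a reader might infer:

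- **That the protocol leaves the order of vital signs and dosing wholly open, so that readings will be an arbitrary pre-dose and post-dose mix.** The documents do not support this, because the default order can be derived.
- **That every patient will lose five doses, including the first.** The documents do not support this either. Specific text requires the doses at V2, at V3 for patients under 16, and at V6, and a site would have to override it.

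The clinical stake should not be overdrawn. Section 5.3 links MC4R activation to blood pressure and heart rate, but Section 4 reports that setmelanotide did not raise either in obese monkeys. The SAP uses vital signs descriptively only.

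What the reply cannot supply is a sentence that limits the prohibition. The intended meaning has to be assembled from three sections, and the sentence passed to patients says something else.

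**Conclusion.** The point holds as an inconsistency between current operative instructions. The texts conflict as worded at all 5 scheduled on-treatment visits and at Bridging Visits. The figure of 5 of 113 dosing days (4.4%) is a ceiling that assumes a site applies Section 11.13 literally at every visit. Omission is less plausible where a specific dose is named, which leaves 2 or 3 scheduled visits depending on age. The documents give no basis for estimating how many sites would read it literally, so omitted doses are a possibility and not a prediction.

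A pre-dose reading is implied but not stated where sites look for it, so the vital-sign summaries lack an explicit time relative to dose. A reader might infer a threat to the primary weight endpoint. The check does not support that: V6 stays within the analysis window, and any omitted doses would be single days about four weeks apart. This assumes that such isolated omissions do not materially change weight at 16 weeks; the documents have no data on that. The correction is worth making because it is cheap and concerns dosing instructions, but it does not alter the main analysis.

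**What to change.** The sponsor should reconcile the Section 11.13 sentence with Table 3 footnotes 26 and 29, Section 7.1, the order of assessments in Section 11 and the sampling rule in Section 11.18. One consistent statement of visit-day dosing relative to vital signs should then apply throughout. Which instruction is right is for the sponsor to decide. The Vitals row of Protocol Table 3 and SAP Table 2 should be marked to match, and SAP Section 4.6.4 should state the resulting time relative to dose for its summaries. The cost is one sentence and one footnote marker in a protocol clarification, with the matching marker and a short phrase in the SAP. Assessments, visits and sample size do not change.
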